In pilot data we tested 12 variables for mean change following training and estimated effect sizes for the set of variables that were significant at a 10% false discovery rate (FDR). The equivalent alpha level for a 10% FDR in our set of pilot data was estimated to be 0.055to account for the potential increase in false positives due to the multiple tests, and the minimum effect size for the set of variables that satisfied the FDR level was 0.6 standard units. Using the pilot data estimate of an FDR-equivalent alpha level we calculated power for a range of effect sizes and for a sample size of N=60 (shown in figure below).

Given the parameters specified above, the figure shows a power level of at least 0.60 when the effect size is at least 0.7 standard units. Based on our pilot data we expect to be sufficiently powered, with multiple testing accommodation, using N=60 subjects for tests of mean change.

7. Sources of Research Material

Materials obtained for research purposes include demographic information, survey/questionnaire data, neuropsychological testing battery, brain imaging MRS 7T data, genetic data and sleep data in cognitively normal adults and mild cognitive impairment. A swab of the cheek/saliva will be collected for a DNA sample. All of the data will be obtained for research purposes.

8. Potential Risks:

Neuropsychological assessment risk: There are no known risks associated with the neuropsychological testing other than possible fatigue and frustration. If the participants feel tired they will be allowed to rest. If they become frustrated, they can rest or stop participation at any time.

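### Section 6 claims adequate power from a pilot effect selected on significance and taken from a different intervention; at face value, the design that matches its power figure has power of about 0.47

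*Combined protocol and SAP*

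**What the plan says.** Section 6 (Sample Size) builds its case in four steps.

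- **Source of the effect.** "In pilot data we tested 12 variables for mean change following training". The investigators then "estimated effect sizes for the set of variables that were significant at a 10% false discovery rate (FDR"), and "the minimum effect size for the set of variables that satisfied the FDR level was 0.6 standard units".
- **Alpha.** A level of 0.055 is taken as equivalent to that filter in the pilot data. Sidedness is not stated.
- **Power.** Using that alpha, "we calculated power for a range of effect sizes and for a sample size of N=60". The result quoted is "a power level of at least 0.60 when the effect size is at least 0.7 standard units".
- **Conclusion.** "Based on our pilot data we expect to be sufficiently powered, with multiple testing accommodation, using N=60 subjects for tests of mean change".

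The pilot's sample size, population, outcomes and standard deviations are not given, nor are the effects of any variables that failed the filter.

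Elsewhere, Section 1 sets out Goals 1 to 3 as comparisons and associations across cognitively normal, MCI and AD groups, and Section 3 plans 20 per group. Section 4 has the spectroscopy scan done once. The only intervention is the oral appliance. Under Sections 2 and 4, a participant reaches it by showing clinically significant snoring, choosing treatment and being found suitable by the dentist. The expected number is not stated.

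**The concern.** Three things undermine the conclusion.

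1. **Selection.** Effects read only from variables that reached significance tend to overstate the truth, because a variable with an unluckily low estimate drops out.
2. **Transfer.** A within-person change after training is a different quantity from a difference between diagnostic groups at one time, and from a change after an oral appliance. The pilot says nothing direct about either.
3. **Face value.** Power of 0.60 is modest, and it is quoted at 0.7 SD, above the pilot minimum of 0.6 SD on which the expectation leans.

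This is the document's only assurance about power. If it stands, a null result on the metabolite, sleep or gene comparisons could be read as evidence of no difference from an adequately sized study, when the design could easily miss differences of the size considered.

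**Working it through.** **Inputs.** Alpha 0.055, N = 60, power at least 0.60 at 0.7 SD and pilot minimum 0.6 SD (all Section 6); 20 per group (Section 3). Assumed: two-sided tests, equal variances, no dropout.

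**Step 1: reproduce the stated power.** For two groups of n, the noncentrality is d × √(n/2) on 2n − 2 degrees of freedom. With n = 20 and d = 0.7 it is 0.7 × √10 = 2.214. The critical value t(0.9725, 38) is 1.980, and the noncentral t gives power **0.595** (0.616 by the normal approximation). Other layouts at 0.7 SD and alpha 0.055:

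| Layout | Power |
|---|---|
| Paired change, all 60 | over 0.99 |
| Paired change, 20 | 0.855 |
| 30 vs 30, two-sided | 0.773 |
| 20 vs 20, one-sided | 0.718 |
| 20 vs 20, two-sided | 0.595 |
| Three-group F test, 20 each, extreme groups 0.7 apart | 0.49 to 0.62 |

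Of the paired and two-group layouts, only 20 vs 20 two-sided agrees with 0.60. The F test agrees only in its most favourable pattern, with one group 0.7 SD from the other two. The quoted figure is not that of a mean-change test in 60 people, although the text describes it that way.

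**Step 2: power of the matching design at other effects.** Same formula, 20 vs 20, two-sided 0.055:

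| True difference (SD) | Noncentrality | Power |
|---|---|---|
| 0.7 | 2.214 | 0.595 |
| 0.6 | 1.897 | 0.473 |
| 0.5 | 1.581 | 0.354 |
| 0.4 | 1.265 | 0.248 |
| 0.3 | 0.949 | 0.163 |

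The favourable F-test pattern does not rescue it. With group means 0, 0 and 0.6 the noncentrality is 20 × (0.2² + 0.2² + 0.4²) = 4.8 on 2 and 57 degrees of freedom, giving power 0.48.

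**Step 3: the mean-change reading.** For paired data the noncentrality is d × √n. With all 60, power is 0.996 at 0.6 SD and 0.87 at 0.4 SD. Phase 2 uptake is not stated, so a range is shown at 0.6 SD: 0.415 for 10 participants, 0.736 for 20, 0.896 for 30 and 0.963 for 40.

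**Step 4: can the selection bias be sized?** Assume a paired pilot, 12 independent variables with a common true effect, and a fixed threshold of 0.055. The average smallest significant effect is then:

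| Assumed pilot n | True effects 0.3 to 0.5 |
|---|---|
| 13 | about 0.66 to 0.70 |
| 20 | about 0.50 to 0.53 |
| 30 | about 0.40 to 0.41 |

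At a true effect of 0.5 the minimum is too high with 13 subjects, about right with 20 and too low with 30. A second check assumed Benjamini-Hochberg selection, pilot sizes of 13 to 30 and three assumed effect distributions. When the observed minimum was near 0.6, the true effect of that variable averaged 0.36 to 0.54. Optimism is therefore plausible, but its amount depends on facts that are not given.

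**Step 5: precision.** The 95% confidence interval half-width for a pairwise difference is t(0.975, 38) × √(2/20) = 2.024 × 0.316 = **0.64 SD**.

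**The case against.** The strongest reply has four parts.

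- **The bias is not demonstrated.** This stands. Taking the minimum of the selected set partly offsets the selection, and Step 4 shows that the bias can vanish or reverse. The stated alpha also gives some evidence against very small effects. If Benjamini-Hochberg was used, a threshold of 0.055 over 12 tests implies 0.055 × 12 / 0.10 = 6.6, so about 6 or 7 variables passed. In a simple model with 13 pilot subjects and a common effect, that many pass in under 1% of pilots at a true effect of 0.3, but in 30% at 0.6. A reader might infer that 0.6 SD is simply the pilot's significance cut-off, or that it is inflated by some definite factor. The documents support neither, since the pilot size is not given.
- **Power is not quoted at 0.6 SD.** Correct: Section 6 uses a range and quotes 0.7 SD. But it then rests its expectation on the pilot data, whose reported minimum is 0.6 SD, where the matching design does worse.
- **The text says mean change, and a paired test in 60 is powerful.** True as arithmetic, but it does not give the stated 0.60, and the plan does not provide 60 paired observations. Goals 1 to 3 use no change score, and Phase 2 takes a subset. With high uptake a Phase 2 test could be well powered at 0.6 SD, but the plan gives no basis for assuming that.
- **The study calls itself a pilot.** This stands as a defence of its size. Low power is no fault in exploratory work. The fault is claiming adequacy.

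**Conclusion.** The concern holds in this form: the assurance of power is not supported, for two separate reasons.

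First, the pilot effect was selected on significance and follows an intervention that this study does not give. It may be optimistic, and it is not shown to transfer to the group comparisons or to the oral appliance phase. The selection and the difference in intervention are both plain in the text. The direction of any bias is an expectation and its size is unknown.

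Second, and with no argument about bias, the design that matches the stated 0.60 at 0.7 SD has power 0.47 at 0.6 SD, falling to 0.16 at 0.3 SD. This rests on reading the test as a two-sided 20 vs 20 comparison with no dropout.

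A reader might go further and infer that true effects are really 0.3 to 0.5 SD. Nothing in the documents says so; those values show sensitivity only.

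The point should be corrected, but it concerns what the plan claims about the study, not whether the study can go ahead.

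**What to change.** In Section 6:

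1. Delete the statement "Based on our pilot data we expect to be sufficiently powered" and the rest of that sentence.
2. State that the pilot effects are changes after training and were chosen because they were significant. Report the effects of all 12 variables, with the pilot's sample size and the standard deviation used to scale them.
3. Name the test to which the power figure belongs. For the 20 vs 20 contrast, two-sided at 0.055, show power over 0.3 to 0.7 SD: 0.16, 0.25, 0.35, 0.47 and 0.60.
4. Add the precision that the design delivers, a 95% confidence interval half-width of about 0.64 SD per pairwise difference, and present the study as exploratory on that basis.
5. For Phase 2, give an expected number of participants, or show power for change over a range of uptake.

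The cost is a rewritten section and a less favourable stated power. No extra participants, visits or measurements are needed.

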Finally, based on an "improving sleep first hypothesis", a dental intervention (MyTAP; midline traction oral appliance (OA) therapy) will be offered to participants presenting with abnormal sleep and upper airway obstruction parameters. Therapeutic intervention to attenuate upper airway obstruction in sleep by using continuous positive airway pressure (CPAP) was shown to also improve cognitive functioning in AD patients with OSA(Cooke et al. 2009). In most cases, upper airway obstruction can also be acutely corrected using a simple fitted, clinically proven, FDA-cleared midline traction design oral appliance to restore sleep quality and possibly improve cognition and 'normalize' BEM. There are currently no reports on the efficacy of oral appliance therapy to improve daytime sleepiness, objective sleep measures and cognitive function in patients with MCI or AD. The MyTAP is similar to other midline traction design oral appliances which has been in clinical use for over 20 years without any serious adverse effects in treating patients with primary snoring to severe sleep apnea. (Gershman 2002; Hoekema et al. 2008) The MyTAP oral appliance will be used in accordance with its indications for use and FDA-approved labeling. The safety and efficacy of the midline traction oral appliance has already been published. (Thornton & Roberts 1996) As per FDA cleared label MyTAP® OA family of intra-oral appliances are intended for the treatment of night-time snoring and mild to moderate obstructive sleep apnea in patients 18 years or age or older.

The study will be concluded in two phases. In Phase-1, eligible participant will complete a set of neurocognitive testing, genetic sample collection, sleep assessment, and MRS scan. If participant is interested in dental intervention they will progress to Phase-2. In Phase-2 of the study, subjects will complete the dental intervention for 3 months followed by neurocognitive testing and sleep assessment.

3. Summary of the Project

This study will investigate:

1. Brain energy metabolites ratio (energy and phospholipids metabolites)

2. Sleep quality index and its relationship with the performance of episodic memory, attention, language, and executive functions (abstraction, reasoning, verbal fluency, working memory) in three groups: cognitively normal adults, MCI, and AD.

3. Genetic components of APOE £4 and ABCA7

4. Effects of dental intervention in individuals with abnormal sleep parameters and cognition.

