We will recruit up to 60 individuals in three groups of twenty each (20, Cognitively normal, 20 with MCI, and 20 AD) between the ages 55-85 years old. The individuals will be recruited from Dallas- Fort Worth areas through advertisements, flyers, social media, word of mouth, and those from the Center for BrainHealth who had expressed interest in future studies. Interested individuals will complete a study screen for medical history, demographics and memory questionnaire called Clinical Dementia Rating (CDR) scale.

A waiver of consent is being requested to cover potential subjects with a diagnosis of Alzheimer's disease as they participate in the phone screen (including an MRI safety screen) and an initial Clinical Dementia Rating (CDR) scale to assess their ability to provide written informed consent for study participation. If they receive a score of 1 or less, they will be deemed competent to provide their own written informed consent and will proceed to the second part of the competency screen. The potential subject will then be provided a summary of the study and will have their understanding assessed via a short quiz using the competency questionnaire. They have to answer all the questions on this questionnaire appropriately to deemed competency. They will also undergo an initial Mini Mental Status Exam. If they receive a score of 20 or above on the MMSE, they will be deemed competent to provide independent informed consent, and will continue the consent process to provide full written informed consent for study participation.

An alteration of consent and a waiver of documentation of consent are being requested to cover potential subject with normal cognition or mild cognitive impairment, and the phone screen (including an MRI safety screen) for eligibility purposes. If these individuals are deemed eligible to participate in the study, they will be invited to the study site to provide full written informed consent to participate in the study.

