c. Magnetic resonance spectroscopy (MRS): On the same or separate days, the participants will have MRS at 7Tesla at one point of time during which they will lie in the scanner while images of their brain will be recorded for one and half (1.5) hours. In the scanner the participants will be asked to be awake in the scanner, with head placed in a pad-cushioned coil. The volume coil $1H/^{31}P$ MRS imaging data will be acquired using the 7Tesla human MRI scanner at UT Southwestern Medical Center (UTSW). During the MRS data acquisition, subjects will be positioned head-first and supine in the MRI scanner, with the back of the head positioned to rest in the head coil. After preparatory imaging scans, which will be is mainly for localization and shimming, the ³¹P MRS data acquisition will be followed, which will include two surveying scans for evaluation of shimming quality on ³¹P spectra and of ³¹P excitation profiles along HF direction, then a six-slice 2D Chemical Shift Imaging(CSI) scan over the whole brain. For survey MRS scans, standard pulse-acquire technique will be used. Typical parameters are TR 4 s, sampling points 4 K, zero-filled to 8 K prior to FT, post-pulse delay 0.5 ms to filter out the broad phospholipids ³¹P signal. For CSI, slice-thickness will be 2 cm along LR direction, 4-6 slices, TR = 1 sec, NA = 4, sample points 2 K in-plane resolution 2x2cm², scan time ~45 min. After ³¹P MRSI data acquisition, voxel-by-voxel data analysis will be carried out to compare the regional difference in relative concentration of the phosphoryl metabolites; and all the measurements will be calculated from these values.

d. Sleep quality assessment (Figure 1, 2) SleepImage (MyCardio, LLC, Broomfield, CO) recorder collects data on electrocardiogram (ECG), actigraphy, body position, snore, ECG-derived respiration, HRV, HR. The SleepImage system includes a sleep recorder that is clinically validated and FDA cleared to allow the non-intrusive collection of objective measures of sleep quality. The participant will complete the sleep study for four (4) consecutive nights using the device along with self-assessment of sleep by answering the PSQI questionnaire for each night.

The sleep data will be analyzed by [name] and [name].

Figure 1: SleepImage sleep device in recording position.

[figure not shown]

Figure 2: SleepImage sleep device actual size.

Total time committed towards research will be around 37 hours excluding the time for transit.

Dental Intervention:

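### Section 6 carries an alpha of 0.055 over from pilot data as this trial's multiplicity allowance without justification, so its claim that multiple testing is covered is unsupported

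*Combined protocol and SAP*

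**What the plan says.** Section 6 (Sample Size) starts from other data: "In pilot data we tested 12 variables for mean change following training". The level matching a 10% FDR in those data "was estimated to be 0.055to account for the potential increase in false positives due to the multiple tests". The section then applies that level to this trial: "Using the pilot data estimate of an FDR-equivalent alpha level we calculated power for a range of effect sizes". It reports power of at least 0.60 at 0.7 standard units or more with N=60, notes that the smallest effect among the FDR-significant pilot variables was 0.6, and concludes: "we expect to be sufficiently powered, with multiple testing accommodation, using N=60 subjects for tests of mean change".

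The rest of the protocol describes a different set of tests:

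- **Goals.** In Section 1, goals 1 to 3 are three-group comparisons and associations among metabolite ratios, sleep quality, two genes and cognition. Only goal 4 concerns change after the dental appliance.
- **Groups.** Section 3: "We will recruit up to 60 individuals in three groups of twenty each".
- **Imaging.** Section 4c: "the participants will have MRS at 7Tesla at one point of time".
- **Change scores.** Section 2: "If participant is interested in dental intervention they will progress to Phase-2". There the appliance period is "followed by neurocognitive testing and sleep assessment", with no second scan mentioned. Section 4 (Dental Intervention) further limits this subset to participants who snore above a threshold, choose the device and are judged eligible by the dentist.

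The documents contain no list of tests for this trial, no FDR or other adjustment procedure for its analysis, and no argument that its tests resemble those in the pilot data.

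**The concern.** The alpha that corresponds to a given FDR is not a constant. It depends on how many of the tested effects are real and how well they are detected, so it describes one set of p-values. A value read off 12 change scores after training has no automatic standing for group contrasts and associations, or for change after an oral appliance in a self-selected subset. Nor is 0.055 stricter than the conventional unadjusted 0.05, so by itself it adds no protection.

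At stake is how results will be read. Section 6 tells the reader that multiplicity has been dealt with. Someone relying on that could treat an uncorrected p-value below 0.055 as already adjusted.

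**Working it through.** **Inputs.** From Section 6: alpha 0.055, 10% FDR, 12 pilot variables, N=60, effects of 0.7 and 0.6 SD, power of at least 0.60. From Section 3: three groups of 20. Assumptions, because the plan is silent: two-sided t tests, independent tests, every real effect equal to 0.7 SD, and a share p of effects that are real.

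**1. The stated power.** Noncentral t at alpha 0.055 and 0.7 SD:

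- 20 v 20: noncentrality 0.7 × √(20/2) = 2.21 on 38 df, power 0.595.
- 30 v 30: power 0.773.
- Paired, n=20: power 0.855.
- Paired, N=60: noncentrality 0.7 × √60 = 5.42 on 59 df, power 0.9997.

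Of these four, 20 v 20 comes closest to 0.60. The match is numerical only, since the section names tests of mean change and states a lower bound.

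**2. What 0.055 implies in the pilot data.** The FDR method is not named. Under Benjamini-Hochberg (BH, assumed), the cut-off for k rejections out of 12 is k × 0.10/12, which is 0.0500 for k=6 and 0.0583 for k=7. So 0.055 corresponds to 0.055/0.10 = 55% of tests rejected, or 6.6 of 12. Nothing says that this trial's tests will behave similarly.

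**3. FDR if 0.055 is held fixed.** In the many-test limit,

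FDR = 0.055(1−p) / [0.055(1−p) + power × p].

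Example, 20 v 20 at p=0.30: 0.0385 / (0.0385 + 0.1786) = 0.177.

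| Share real | 20 v 20 (power 0.595) | Paired, N=60 (power 0.9997) |
|---|---|---|
| 50% | 8.5% | 5.2% |
| 30% | 17.7% | 11.4% |
| 20% | 27.0% | 18.0% |

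For a family of only 10 independent tests, simulation gives lower values: 7.2%, 14.2% and 20.0% for 20 v 20, and 4.5%, 9.0% and 13.3% for paired N=60.

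**4. Break-even share.** Setting FDR = 0.10 in the same formula gives p = 0.0495 / (0.0495 + 0.1 × power).

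- 20 v 20: 0.0495 / (0.0495 + 0.0595) = 0.454.
- Paired, N=60: 0.0495 / (0.0495 + 0.09997) = 0.331.

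**5. Power at a true 10% FDR, 20 v 20.** Solving the formula in step 3 for the alpha that gives exactly 10%:

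- 50% real: alpha 0.071, power 0.64, so no shortfall.
- 25% real: alpha 0.0135, power 0.37.

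The required alpha falls below 0.055, and power below 0.595, only when p is under about 45%. Plain BH at q=0.10 gives a lower power of 0.452 at 50% real (alpha 0.0238), but there it holds FDR at (1−0.5) × 0.10 = 5%, half the target.

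**6. Paired change with N=60.** Even at the strictest BH step for 12 tests, 0.10/12 = 0.0083, power at 0.7 SD is 0.996.

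**7. Unadjusted power for one 20 v 20 contrast at alpha 0.05.** 0.578 at 0.7 SD and 0.456 at 0.6 SD.

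**The case against.** The strongest reply is that 0.055 may serve well enough. If about half of this trial's effects are real, as the pilot data might suggest, holding it fixed gives an FDR of 5% to 8.5%, inside the 10% target. For the test that Section 6 names, a mean change with N=60, power is above 0.99 under any plausible adjustment. The study also calls itself a pilot, and goal 1 is framed as exploration.

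Much of this stands, and it rules out two stronger readings that a reader might infer:

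- **That 0.055 is wrong, or that the trial is underpowered once multiplicity is handled.** The documents give no share of real effects, so neither follows. The drop to 0.45 for 20 v 20 at a 50% share reflects the conservatism of plain BH, not a failure to meet 10%. The 20 v 20 reading is itself inferred: a three-group ANOVA with one group shifted by 0.7 SD gives 0.615, and paired N=60 also satisfies a lower bound of 0.60. The power figure is not available in the extracted text.
- **That no metabolite test could ever be a test of change.** Section 1 also states an aim to see whether dental intervention improves the brain's metabolic rate. That conflicts with the single scan in Section 4c and the Phase-2 content in Section 2, and the passages need reconciling. As the procedures stand, metabolites are measured once.

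The reply does not supply the missing justification. Whether 0.055 is adequate depends on a quantity the plan never states. Moreover, N=60 change scores would require every participant to enter Phase-2, which the eligibility and opt-in conditions do not provide for.

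**Conclusion.** The concern holds as a lack of support. Section 6 asserts a property, allowance for multiple testing, that rests solely on a borrowed cut-off looser than 0.05.

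How much this matters depends on the unstated share of real effects. With many independent tests and real effects of 0.7 SD, fixed 0.055 meets a 10% FDR at or above a share of about 45% (20 v 20) or 33% (paired, N=60) and exceeds it below those shares; small families are somewhat more favourable. No power shortfall is shown for a paired change with N=60. For 20 v 20 contrasts, a shortfall at a true 10% FDR arises only below about 45%.

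Confidence is high that the transfer is unsupported. The FDR and power figures are only as good as the assumptions behind them. Severity is modest because the study is a pilot and the repair is mostly wording.

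**What to change.** **Minimum change, Section 6.** Delete the clause claiming that multiple testing is accommodated, and stop using 0.055 as the multiplicity allowance. State power by test type, for example: *For one 20 v 20 group contrast at two-sided alpha 0.05, power is about 0.58 at 0.7 SD and 0.46 at 0.6 SD; no allowance for multiple testing is included.* Give the association tests their own figure.

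Give goal 4 a paired figure for the number expected in Phase-2. The plan does not state that number. For assumed sizes, paired power at two-sided alpha 0.05 is:

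| Phase-2 n (assumed) | 0.7 SD | 0.6 SD |
|---|---|---|
| 12 | 0.60 | 0.47 |
| 20 | 0.84 | 0.72 |
| 30 | 0.96 | 0.89 |

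**If multiplicity control is to be claimed.** The minimum change withdraws the claim but supplies no control. To claim it, list the tests within each goal before analysis, apply Benjamini-Hochberg at q=0.10 to this trial's own p-values within each goal, and report FDR-adjusted power with the assumed share of real effects stated.

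**Cost.** There are no extra participants or data. Stated power at 0.7 SD moves from 0.60 to 0.58. The fuller option adds a test list and a short simulation; fewer results may reach significance, and control within each goal is not joint control across goals.

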Title of the Protocol: Brain Energy Metabolism and Sleep in Adults Principal Investigator: [name]. Funding Sponsor: UT Dallas Institutional Funding Version 5, September 1st 2018

Abbreviations

AD: Alzheimer's disease MCI: Mild Cognitive Impairment ATP: Adenosine Tri-Phosphate pH : Potential of Hydrogen Mg2+: Magnesium PET: Positron Emission Tomography SPECT: Single-photon emission computed tomography MRS: Magnetic Resonance Spectroscopy 1H MRS: Proton Magnetic Resonance Spectroscopy 31P MRS: Phosphorus Magnetic Resonance Spectroscopy NAA: N-acetyl aspartate PMEs: Phosphomonoesters PDEs: Phosphodiesters Pcr: Phosphocreatine Pi: Inorganic phosphate NTPs: Nucleotide Triphosphate NDPs: Nucleotide Diphosphate MMSE: Mini-Mental Status Examination CVLT: California Verbal Learning Task DKEFS: Delis- Kaplan Executive Function System CDR: Clinical Dementia Rating Scale WAIS: Wechsler Adult Intelligence Scale TOSL: Test of strategic learning COWAT: Controlled Oral Word Association Test BNT: Boston Naming Test DSFB: Digit Span Forward and Backward **APOE** Apolipoprotein ABCA7 ATP binding cassette-A7

Contents

- 1. Introduction and Purpose
- 2. Background
- 3. Summary of the Project
- 4. Study Procedures
- 5. Criteria for Inclusion and Exclusion of subjects
- 6. Sample size
- 7. Sources of research material
- 8. Potential Risks
- 9. Participant safety and data safety monitoring plan
- 10. Potential benefits
- 11. Incentive
- 13. References

1. Introduction and Purpose

The main purpose of this study is to understand the impact of brain energy metabolites (BEM), sleep patterns and specific genes on the performance of neurocognitive measures of memory, attention, language and complex executive functions in cognitively normal adults, in preclinical stages of Alzheimer's disease (AD) i.e., mild cognitive impairment (MCI), and Alzheimer's disease. The secondary goal is to investigate if sleep and cognition could be improved in the three cohorts with dental intervention to correct the airway.

The three primary goals of this pilot will be followed by a secondary goal to test if dental intervention improves brain health in terms of brain's metabolic rate and cognition. The primary and secondary goals are

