1. Explore the ratios of brain energy (ATP/PCr, Pi/PCr) and phospholipids (PME/PDE) metabolites as measured by magnetic resonance spectroscopy at 7 Tesla, and compare the differences in them with the performance of episodic memory, attention, language, and executive functions (abstraction, reasoning, verbal fluency, working memory) in three groups: cognitively normal adults, MCI and AD.

2. Investigate the differences in sleep patterns measured by the ratio sleep quality index (Stable/ Unstable sleep) in cognitively normal adults, MCI and AD and its relation to the performance of episodic memory, attention, language, and executive functions (abstraction, reasoning, verbal fluency, working memory) in three groups.

3. Investigate the differences in the variations of two genes, APOE-E4 and ABCA7, in relationship to the changes in the brain energy metabolites and its relation to the performance of episodic memory, attention, language, and executive functions (abstraction, reasoning, verbal fluency, working memory) in those with cognitively normal adults, MCI and AD.

4. Investigate if dental intervention improves sleep patterns and overall cognitive behavior in the three cohorts.

2. Background

Alzheimer's disease (AD) is rapidly progressing in the elder population and the pathophysiological changes in the brain starts at least 1-2 decades before the disease onset. During this period of slow progression individuals may notice subtle changes in the memory and this subset of population are termed as Mild Cognitive Impairment (MCI)._MCI is a pre-clinical stage of Alzheimer's disease (AD) in which individuals have memory complaints but are functionally independent and not yet clinically diagnosed with dementia[39]. New modalities for potential identification of the progression of the disease, includes different biomarkers, state-of-the-art technologies like sleep tracking and magnetic resonance spectroscopy (MRS) may provide an additional, important tools to facilitate early detection of disease, which may allow for earlier intervention and provide a potential gauge for response to treatment.

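### Section 6 claims sufficient power for mean change with N=60, but the design does not provide 60 change scores and gives no Phase-2 sample size

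*Combined protocol and SAP*

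**What the plan says.** Section 6 starts from pilot data in which "we tested 12 variables for mean change following training". It takes two inputs from that pilot. The first is an alpha of 0.055: "The equivalent alpha level for a 10% FDR in our set of pilot data was estimated to be" that value. The second is an effect size: "the minimum effect size for the set of variables that satisfied the FDR level was 0.6 standard units". For N=60 it then reports that "the figure shows a power level of at least 0.60 when the effect size is at least 0.7 standard units", and concludes that "we expect to be sufficiently powered, with multiple testing accommodation, using N=60 subjects for tests of mean change".

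Elsewhere the plan describes the following.

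- **Enrolment (Section 3):** a maximum of 60 people, in three cohorts of 20 (cognitively normal, MCI, AD).
- **Order of goals (Section 1):** "The three primary goals of this pilot will be followed by a secondary goal to test if dental intervention improves brain health". Goals 1 to 3 concern differences between cohorts, genotype, and relations with cognitive performance. Only Goal 4 concerns change: "Investigate if dental intervention improves sleep patterns and overall cognitive behavior in the three cohorts".
- **MRS (Section 4, item c):** a single scanning occasion.
- **Second measurements (Sections 2, 3 and 4):** neuropsychological and sleep assessments only, after the dental intervention.
- **Entry to Phase 2:** it depends on choice (Section 2): "If participant is interested in dental intervention they will progress to Phase-2". It also depends on the sleep recording (Sections 3 and 4) and on the dentist finding the person eligible (Section 4, Dental Intervention).

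No expected Phase-2 number, uptake rate or dropout allowance is given.

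**The concern.** A test of mean change needs two measurements per person. Section 6 counts 60 such people, but 60 is the ceiling on Phase-1 enrolment, where each person is measured once. The number with a second measurement is unknown, and for MRS it is zero.

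This is the only quantitative justification for N=60. A reader would conclude that change is tested in 60 people with adequate power. The same reader learns nothing about the power of the cohort comparisons that serve the primary goals. The two pilot inputs add to the difficulty: they describe change after a different intervention, and the plan does not say why they should carry over to an oral appliance or to differences between cohorts.

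**Working it through.** **Step 1. Count the change scores.**

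- MRS: one occasion, so no change scores.
- Cognition and sleep: change scores = Phase-2 completers. To reach 60, enrolment must hit its ceiling and every participant must qualify on the sleep recording, choose the appliance, be found eligible and complete. The plan does not say that this is expected.

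This step needs no power calculation and does not depend on the power figure.

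**Step 2. Inputs for the power checks.** Alpha 0.055 and effects of 0.6 and 0.7 SD are from Section 6; the cohort size of 20 is from Section 3. The text of Section 6 names no test or sidedness. Two-sided t tests are assumed here unless stated.

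Power = P(T > c) + P(T < −c), where T is noncentral t with noncentrality δ and c is the 1 − 0.055/2 quantile of central t.

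- One-sample change: δ = d√n, df = n − 1.
- Two groups of n: δ = d√(n/2), df = 2n − 2.

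**Step 3. The plan's own figure (at least 0.60 at 0.7 SD).**

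- As worded, change in 60: δ = 0.7 × √60 = 5.422, df = 59, c = 1.958, power 0.9997. At 0.6 SD, δ = 4.648 and power is 0.996. Both satisfy the printed lower bound but lie far above it.
- Two cohorts, 20 versus 20: δ = 0.7 × √10 = 2.214, df = 38, c = 1.980, power 0.595. This is close to 0.60.
- The match is not unique. Twelve pairs give 0.618, and a three-group F test with one cohort apart gives 0.615.

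**Step 4. If the 0.60 refers to 20 versus 20.** At the pilot minimum, δ = 0.6 × √10 = 1.897 and power is 0.473. Power of 80% is reached at about 0.89 SD.

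**Step 5. Change in Phase 2.** The number of completers is an assumption. Figures are one-sample, two-sided, alpha 0.055, pooled over cohorts.

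| Completers | Power at 0.6 SD | Power at 0.7 SD | Mean change with 80% power (SD) |
|---|---|---|---|
| 10 | 0.415 | 0.526 | 0.98 |
| 15 | 0.599 | 0.729 | 0.76 |
| 20 | 0.736 | 0.855 | 0.65 |
| 30 | 0.896 | 0.963 | 0.52 |

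The smallest number of completers giving power of at least 0.60 at 0.7 SD is 12 (0.618; 11 give 0.574). One-sided at 0.055 it is 9 (0.629; 8 give 0.578). Power of 80% needs 24 completers at 0.6 SD and 18 at 0.7 SD, two-sided.

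**The case against.** **The printed power statement is not contradicted.** This stands. Section 6 gives a lower bound, and 0.9997 meets it. A reader might infer from the gap between 0.9997 and 0.60 that the calculation is wrong, or that it was really done for 20 versus 20. The documents do not support either inference. The power curve was not available in the text we worked from and may name the test, and several setups give about 0.60. Power of 0.47 at 0.6 SD is therefore conditional on the 20-versus-20 reading. On the literal reading it is 0.996.

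**Phase 2 may be adequately powered.** This also stands. Pooled over cohorts, 18 to 24 completers would give 80% power at 0.7 to 0.6 SD. A reader might infer that the change analysis is underpowered; the plan gives no number from which to conclude that.

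**The 20-versus-20 figures do not cover all primary goals.** Correct. Goal 3 concerns genotype, for which no carrier numbers are given, and Goals 1 to 3 all ask about relations with cognition. A two-group standardized difference between cohorts of 20 describes neither.

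**This is a pilot with exploratory goals and no power target.** True, and it limits the weight of the point. The 80% level used here is only a reference. But a pilot need not claim power; this one does, and the claim is the conclusion of its sample-size section.

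None of these objections supplies the missing second measurements or the missing Phase-2 number.

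**Conclusion.** The sufficiency claim is wrong as written. N=60 is not the sample size for any planned test of mean change. It is zero for MRS, and for cognition and sleep it is an unstated subset of at most 60. That conclusion rests on the text alone.

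The size of the effect on power depends on the unstated number. At 0.6 SD, pooled and two-sided at alpha 0.055, power runs from 0.415 with 10 completers to 0.896 with 30, against 0.996 if all 60 had change scores. These figures also assume that the pilot effect and alpha apply to the oral appliance, which the plan does not show.

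The finding does not extend to saying that Phase 2 is too small, that the 0.60 is miscalculated, or that the primary goals as a whole have power of 0.47. It should be fixed, and the fix does not touch the conduct of the study.

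**What to change.** In Section 6:

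1. Delete the sentence claiming sufficient power for mean change with N=60. If the figure does not already do so, name the test, sidedness and n behind the 0.60.
2. For Goal 4, state the expected number of Phase-2 completers and whether cohorts are pooled or compared, and give the power for that number. If pooled, the last column of the table gives the change detectable with 80% power. State that change in MRS measures is not tested; the introduction to the goals in Section 1 names metabolic rate as a target of the dental intervention and should be brought into line.
3. For pairwise cohort contrasts in Goals 1 and 2 only, state that 20 versus 20 (two-sided, alpha 0.055) has power of about 0.47 at 0.6 SD and 0.60 at 0.7 SD, with 80% at about 0.89 SD. Say why 0.055 applies to these contrasts. Do not attach these figures to the genotype contrasts of Goal 3 or to relations with cognition.
4. Describe 0.6 SD as the smallest effect among the selected pilot variables after a different intervention, not as the effect expected here.

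The cost is protocol wording; participants, data and analysis are unchanged. The broad claim of sufficient power for change is withdrawn, and the figures for the cohort contrasts are modest. The stated power for Goal 4 need not fall below 0.60: with 20 pooled completers it would be 0.855 at 0.7 SD.
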